#### 17.2.1. Secondary Efficacy Variables & Derivations

17.2.1.1. PROPORTION OF PASI 50, PASI 75, PASI 90 AND PASI 100 RESPONDERS AT WEEK 28 A PASI 50, PASI 75, PASI 90, and PASI 100 response is defined as a  $\geq$  50%,  $\geq$  75%,  $\geq$  90% and  $\geq$  100% improvement of PASI score from baseline (Week1/ Visit1).

Document: \\ieedc-vnasc01\Biosdata\\Viatris\HULIO\HAB34991\Biostatistics\Documentation\SAP

Author: Version Number: 2.0

Version Date: 29Nov2023

Template No.: CS\_TP\_BS016 Revision 7 Reference: CS\_WI\_BS005

Effective Date: 01Nov2021

Page 29 of 48

=	PASI50	)		a	t			Week				X:
	Yes	if	percent	change	of	PASI	score	at	Week	X	≤	-50
	No if p	ercent (	change of PA	SI score at W	eek X >	-50						
-	PASI75	5		a	t			Week				X:
	Yes	if	percent	change	of	PASI	score	at	Week	X	<	-75
	No if p	ercent (	change of PA	SI score at W	eek X >	-7 5						
-	PASI90	)		a	t			Week				X:
	Yes	if	percent	change	of	PASI	score	at	Week	X	<	-90
	No if p	ercent (	change of PA	SI score at W	eek X >	· - 90						
(17)	PASI10	00		:	at			Week				X:
	Yes	if	percent	change	of	PASI	score	at	Week	X	≤	-100
	No if p	ercent	change of PA	SI score at W	eek X >	-100						

where, percent change of PASI score (%) at Week X = [(PASI score at Week X - PASI score at Baseline)/ PASI score at baseline] x100)).

Example, if percent change of PASI score (%)  $\leq$  - 90 then it would be considered as PASI 90 responder.

### 17.2.1.2. PROPORTION OF SPGA SUCCESS (CLEAR OR ALMOST CLEAR) AT WEEK 28

The sPGA is used to determine the patient's psoriasis lesions overall at a given time point. It will be used to assess the improvement in the overall severity of the disease in individual patients and thus arrive at the number and percentage of patients achieving sPGA responses of clear (0) or almost clear (1).

- sPGA Success at Week X
- Yes, if sPGA response at Week  $X \le 1$
- No, if sPGA response at Week X > 1

#### 17.2.2. Data Imputation for Secondary Efficacy Variable(s)

Missing data will be handled using a combination of non-responder imputation and multiple imputation methods. After applying multiple imputation, non-responder imputation will be performed.

Multiple imputation (MI) is a simulation-based approach where missing values are replaced by multiple Bayesian draws from the conditional distribution of missing data given the observed data and covariates, creating multiple completed data sets. These completed data sets can then be analyzed using standard methods. Rubin (1987) presented rules how to combine the multiple sets of estimates to produce overall estimates and confidence intervals that

Document: \\ieedc-vnasc01\Biosdata\Viatris\HULIO\HAB34991\Biostatistics\Documentation\SAP

Author: Version Number: 2.0

Version Date: 29Nov2023

Template No.: CS\_TP\_BS016 Revision 7 Reference: CS\_WI\_BS005

Template No.: 00\_11 \_D0010 Nevision /

Page 30 of 48

adequately incorporate missing data uncertainty. Below steps will be applied on the PASI score and the sPGA separately.

Step 1: Creation of multiple imputed data sets

The first step of the multiple imputation is to transform a non-monotone missing data structure to a monotone one. Intermediate missing variables will be multiple imputed using the Markov Chain Monte Carlo (MCMC) method and assuming Missing at Random (MAR) and multivariate Normality. The SAS procedure PROC MI with the MCMC option will be used. Missing values for the 'change from baseline PASI score' or 'sPGA score' will be imputed. The change from baseline in PASI score appears to follow closer to a normal distribution than the actual PASI score. Assuming normality for the 'sPGA score' as well. This step will be performed on longitudinal continuous change from baseline PASI score or sPGA score between Baseline and week 28 (Week 12, 16 and 20 inclusive).

For each variable, the imputations will be done separately for each randomized treatment group including baseline weight as additional covariate.

The number of imputations will be set to 500. The SAS code used to generate the multiple imputed data sets will be like that shown below:

The input data set <Efficacy> should have one record per patient with baseline PASI score or sPGA score as well as all changes from baseline PASI or post baseline sPGA score.

(A) - Creation of monotone missing data structure

PROC MI DATA=<Efficacy> OUT=<impdata> SEED=3001 NIMPUTE=500;

VAR <baseline weight> <baseline PASI/baseline sPGA> <change from baseline PASI week X/sPGA week X> - <change from baseline PASI week secondary endpoint/sPGA week secondary endpoint>;

BY <treatment group>;

mcmc chain=single nbiter=1000 impute=monotone;

Run;

(B) - The dataset with monotone missing data will be imputed using regression model by considering the stratification factors and respective timepoints

PROC MI DATA =< impdata > OUT=<Output data> NIMPUTE =1 SEED=3001;

BY IMPUTATION;

CLASS <treatment group>;

VAR <baseline weight> <baseline PASI/baseline sPGA> <change from baseline PASI week X/sPGA week X> - <change from baseline PASI week secondary endpoint/sPGA week secondary endpoint>;

MONOTONE REGRESSION;

Run;

Document: \\ieedc-vnasc01\Biosdata\Viatris\HULIO\HAB34991\Biostatistics\Documentation\SAP

Author: Version Number: 2.0

Version Date: 29Nov2023

Template No.: CS\_TP\_BS016 Revision 7 Reference: CS\_WI\_BS005

Effective Date: 01Nov2021

Page 31 of 48

The imputed data are saved in data set <Outputdata>. The outcomes of interest, i.e., the PASI 90 response or sPGA response will be calculated, e.g. as follows:

DATA <impdata2>;

SET <impdata>;

\*\*\* PASI 90 response

IF <change from baseline PASI week secondary endpoint>/<baseline PASI <= -0.90 THEN <PASI 90

response> =1;

ELSE <PASI 90 response>=2;

\*\*\* sPGA response

IF <baseline sPGA>>=3 THEN DO;

IF <sPGA week secondary endpoint> < 1.5 THEN <sPGA 0/1 response> =1;

ELSE IF <sPGA week secondary endpoint> >= 1.5 THEN <sPGA 0/1 response> =2;

END:

RUN;

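### SAP 17.2.2: the sample code derives Week 28 response from the wrong data set and does not impute by arm, contrary to the SAP's own text

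*SAP*

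**What the plan says.** SAP 17.2.2, Step 1, describes the imputation of PASI change from baseline and of sPGA score in words and then in sample code.

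- **Rule in words.** "For each variable, the imputations will be done separately for each randomized treatment group including baseline weight as additional covariate". MCMC is to fill intermediate gaps only, so that the missing-data pattern becomes monotone.
- **Step A code.** It runs by treatment group, with "mcmc chain=single nbiter=1000 impute=monotone", and writes 500 copies to `impdata`. The Week 28 variable is last in the VAR list.
- **Step B, words and code.** "The dataset with monotone missing data will be imputed using regression model by considering the stratification factors and respective timepoints". The code reads `impdata`, writes a new output data set and runs BY imputation number only. It carries "CLASS <treatment group>", but treatment group is not in the VAR list as printed.
- **Response derivation.** After "The imputed data are saved in data set <Outputdata>", the DATA step opens with "SET <impdata>". It codes PASI 90 response when the change divided by baseline is at or below -0.90. For sPGA it has "IF <sPGA week secondary endpoint> < 1.5 THEN <sPGA 0/1 response> =1".

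The code is introduced as a model and not as the final program: "The SAS code used to generate the multiple imputed data sets will be like that shown below". Appendix 2 points back to section 17.2, so the SAP holds no other version.

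**The concern.** The text and the code give different instructions on two matters that affect the result.

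First, the text places the completed data in the Step B output, but response is derived from the Step A output. Followed as printed, Step B is never used, and patients without a Week 28 score are classed by how SAS sorts missing values, not by an imputation model.

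Second, imputation by arm is required for each variable without exception, but Step B pools the arms. Pooled imputation pulls the arms together, which is the unhelpful direction in an interchangeability study, where a real difference should not be masked.

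A lesser mismatch is that Step B is said to use the stratification factors, yet no term for the Week 12 PASI-response stratum (SAP 8.1) is listed.

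At stake are the Week 28 PASI and sPGA responder rates and their 90% confidence intervals. The SAP has no stated figure that depends on this code.

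**Working it through.** **1. Trace of the data sets**

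| Step | Reads | Writes | State of a missing Week 28 score |
|---|---|---|---|
| A (MCMC, monotone) | `Efficacy` | `impdata` | still missing |
| B (monotone regression) | `impdata` | `Output data` | imputed |
| Response derivation | `impdata` | `impdata2` | still missing |

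Week 28 is last in VAR, so a missing Week 28 score is always a trailing gap, and a monotone fill leaves trailing gaps alone. Over Weeks 12, 16, 20 and 28 there are 2^4 = 16 observed/missing patterns. Week 28 is missing in 8 of them, and in all 8 it is still missing after Step A.

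**2. How the patient is then coded**

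SAS ranks a numeric missing value below any number, so both the PASI condition (at or below -0.90) and the sPGA condition (below 1.5) are true. The patient gets code 1, the level that Step 3 counts. Week 28 is the same in every copy of `impdata`, observed or missing, so response is identical in all 500 and the between-imputation variance is zero.

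**3. Who is affected**

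These are per-protocol patients with no Week 28 score who are not set to non-responder in Step 2. They can exist:

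- SAP 6.5 asks for only one post-randomization assessment of one efficacy endpoint.
- Step 2 resets treatment discontinuation before Week 28, loss to follow-up and severe violations. The last randomized dose is at Week 26 (SAP 3.1). A patient dosed then whose Week 28 score is not recorded, or who then withdraws for a reason other than loss to follow-up, is not clearly covered.
- SAP 7.4 moves early-termination scores off Week 28.

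**4. Size of the miscoding**

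Inputs, all assumed unless a source is given:

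- n = 140 per arm (half of the 280 evaluable in SAP section 4, taken here for the per-protocol population)
- d = 0.08, share set to non-responder in Step 2
- f = 1%, 2% or 5% of the remaining patients missing at Week 28; 140 x 0.92 x f is about 1, 3 and 6 patients per arm
- p = the arm's true response rate

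The affected share of the arm is f(1 - d). Of the arm, f x p would truly have responded. Coding all of them as responders raises the rate by f(1 - d) - f x p = f(1 - d - p).

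| p | f = 1% | f = 2% | f = 5% |
|---|---|---|---|
| 0.48 | 0.44 | 0.88 | 2.20 |
| 0.30 | 0.62 | 1.24 | 3.10 |
| 0.70 | 0.22 | 0.44 | 1.10 |

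(percentage points)

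At p = 0.48 and f = 5%, d = 4% gives 0.05 x 0.48 = 2.4 points and d = 12% gives 0.05 x 0.40 = 2.0. A simulation (2,000 trials per setting) agrees: 0.44, 0.89 and 2.24 points for PASI 90 at 47%, and 0.37, 0.77 and 1.93 for sPGA success at 54%.

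With 2% missing in one arm and 5% in the other, the false difference is 0.03 x 0.44 = 1.3 points (0.03 x 0.22 = 0.7 to 0.03 x 0.62 = 1.9 over the same range of p).

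For scale, the 90% Wald half-width is 1.645 x sqrt(2 x 0.48 x 0.52 / 140) = 9.8 points.

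**5. Pooled against by-arm Step B**

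The same simulation, for an assumed true PASI 90 difference of about -15 points, gives this shrinkage toward zero:

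| Arms differ | f = 1% | f = 2% | f = 5% |
|---|---|---|---|
| from Week 16 | 0.04 | 0.08 | 0.19 |
| at Week 28 only | 0.13 | 0.24 | 0.60 |

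A simpler simulation with 165 per arm gave -13.2 points by arm and -12.5 pooled at 5% missing, a shrinkage of 0.7. With equal arms there is no material effect in either. Adding treatment as a main effect to VAR brings the result within 0.11 points of by-arm imputation.

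**6. Stratum term**

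For PASI, baseline PASI and the Week 12 change, both in the model, largely carry the stratum. For sPGA, leaving the stratum out changes the difference by at most 0.03 points.

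**The case against.** The code is a template with placeholder names that are not used consistently, and the governing text makes the intended analysis clear, so this is arguably a matter for programming quality control. The slip would also tend to show itself. Zero between-imputation variance is conspicuous in the combined results, and the observed-value tables in SAP 17.2.3 would help expose miscoded patients.

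The affected group may be nearly empty: SAP 6.5 allows exclusion for insufficient efficacy data, Step 2 removes most dropouts, and the end of its third criterion cannot be read in the available text. On the by-arm point, the sentence directly follows the MCMC description, Step A obeys it, and the CLASS line suggests treatment was meant to be in the Step B model. All the sizes above rest on assumed rates, and no passage supports a true arm difference of 15 points.

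Most of this stands as a limit on the size. It does not remove the conflict. A template may be adapted, but it should not contradict the text it illustrates. Step B itself uses `impdata` as input and another name as output, so the response step is not merely using a loose synonym. The by-arm sentence makes no exception for Step B, and a treatment covariate would still not be separate imputation. The stratum point is only wording.

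**Conclusion.** The concern holds and is minor. The data set named in the response step and the BY statement in Step B both conflict with the text of SAP 17.2.2; confidence in that is high.

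Confidence in the size is moderate, because the missing rates, the non-responder share, the response rates and the arm differences are all assumed. Under those assumptions the wrong data set inflates an arm's PASI 90 rate by 0.2 to 3.1 points and, with unequal missingness, creates a false difference of 0.7 to 1.9 points. Pooling in Step B matters only if the arms truly differ, and then by about 0.7 points or less at up to 5% missing. All of this is well inside the 9.8-point half-width. The endpoints are secondary with no margin, and the primary PK analysis is unaffected.

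**What to change.** - Derive response from the Step B output, and leave response missing when the Week 28 value is missing, so that any failure of the imputation shows.
- Sort by imputation number and treatment group, run Step B BY both, and drop the CLASS line, which is then redundant.
- Use one chain of data set names, with Step 3 reading the result of Step 2. Step 3 now reads `Inpdata`, which no earlier step creates; check this name against the source file, as it may be a PDF reading error.
- Optionally, add the Week 12 PASI-response stratum to the Step B model (chiefly for sPGA) or delete the phrase on stratification factors. Nothing material depends on which.

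The cost is a few lines in SAP 17.2.2. No new data are needed, and the primary analysis does not change.

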#### • Step 2: Non-responder imputation

Patients will be considered as non-responder if

- discontinued the study treatment before Week 28
- lost to follow up before Week 28 (As per End of study CRF page)
- any severe violation related to any therapy that may significantly impact efficacy assessment before
   Week 28 (which will be decided during

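### The sample responder code in SAP 17.2.2 reads the Step A file, not the completed Step B file; programmed as printed, a missing Week 28 score can count as a response

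*SAP*

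**What the plan says.** SAP section 17.2.2 handles missing PASI and sPGA scores by multiple imputation followed by non-responder imputation.

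- **Step 1(A)** runs PROC MI with "mcmc chain=single nbiter=1000 impute=monotone", 500 imputations, and writes `<impdata>`. Its stated purpose is to make the missing-data pattern monotone.
- **Step 1(B)** takes `<impdata>` as input: "The dataset with monotone missing data will be imputed using regression model by considering the stratification factors and respective timepoints". The PROC MI statement writes `<Output data>`, and the sentence after the code says "The imputed data are saved in data set <Outputdata>".
- **Response derivation** comes next: "DATA <impdata2>" followed by "SET <impdata>". PASI 90 response is set to 1 when change divided by baseline is at or below -0.90. For sPGA the rule is "IF <sPGA week secondary endpoint> < 1.5 THEN <sPGA 0/1 response> =1", applied when baseline sPGA is at least 3.
- **Step 2** resets patients to non-responder for reasons that include "discontinued the study treatment before Week 28", loss to follow-up before Week 28 and severe violations affecting efficacy.
- **Step 3** runs PROC FREQ on `<Inpdata>` and counts level 1 as response.

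The code is offered as a model: "The SAS code used to generate the multiple imputed data sets will be like that shown below". Appendix 2 contains no other code for these endpoints and refers back to section 17.2.

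**The concern.** The text says the completed data are in the Step B output, but the code a few lines later reads the Step A output. This is not a matter of spacing or spelling. `<impdata>` is a distinct name, used correctly as the output of Step A and the input of Step B.

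Step 2 already sends treatment discontinuations and losses to follow-up to non-response. The patients whose result depends on Step B are therefore mainly those dosed through Week 26, the last randomized dose, who have no usable Week 28 score. The printed line bypasses Step B for exactly these patients. Instead of an imputed value they would receive an automatic success, the opposite direction to the plan's own non-responder rule.

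At stake are the PASI 50/75/90/100 and sPGA response rates at Week 28 and their differences with 90% Wald intervals.

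**Working it through.** The plan states no figure for this point, so the check is a trace of the data flow followed by an illustration of size.

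**1. Does Step A ever fill Week 28?** Monotone filling imputes a value only when a later one is observed. Week 28 is the last variable in the VAR list, so nothing follows it. Of the 2⁴ = 16 observed/missing patterns over Weeks 12, 16, 20 and 28, Step A fills Week 28 in none. Every patient without a Week 28 score is still missing in `<impdata>`.

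**2. What do the IF statements return?** This uses standard SAS behaviour, which the documents do not state: a numeric missing value sorts below every number, and missing divided by baseline is missing.
- PASI 90: missing ≤ -0.90 is true, so response = 1. The ELSE branch is not reached.
- sPGA: missing < 1.5 is true, so response = 1. The condition of baseline sPGA ≥ 3 is met by design, because it is an entry criterion (Protocol synopsis, inclusion criterion 3).

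The result is the same in all 500 datasets. Week 28 response then has no between-imputation variance, and the multiple imputation does nothing for it.

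**3. Does this reach the estimates?** Step 3 names `<Inpdata>`, which no step creates. In the printed code only `<impdata2>` holds a response variable, so it is the plausible input, but the plan does not say so.

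**4. Size.** Let *m* be the share of an arm's analysed patients with no Week 28 score after Step 2, and *p* the response rate a proper imputation would give them. Neither is in the documents; both are assumptions. The overstatement per arm is *m* × (1 − *p*), in percentage points:

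| *m* | *p* = 0.2 | *p* = 0.4 | *p* = 0.7 | *p* = 0.9 |
|---|---|---|---|---|
| 1% | 0.8 | 0.6 | 0.3 | 0.1 |
| 3% | 2.4 | 1.8 | 0.9 | 0.3 |
| 5% | 4.0 | 3.0 | 1.5 | 0.5 |

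High *p* is plausible for PASI 50, since randomization required PASI 50 at Week 12 (SAP 3.1). Low *p* is plausible for PASI 100.

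One affected patient adds 100 × (1 − *p*)/*n* points. At *p* = 0 this is 100/165 = 0.61 with the 165 randomized per arm (SAP 4), or 100/140 = 0.71 with half of the 280 evaluable participants. The latter is a PK count used here as a proxy for the Per Protocol set.

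**5. Effect on the difference.** With equal *m* and *p* in both arms, a zero difference stays zero. With 1 affected patient in one arm and 5 in the other, *n* = 165, the shift is (5 − 1)/165 × (1 − *p*): 1.70 points at *p* = 0.3 and 0.24 at *p* = 0.9.

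For scale, write π for the response rate of the whole arm. The 90% Wald half-width is 1.645 × √(2π(1 − π)/*n*): 5.4 points at π = 0.9, *n* = 165, and 9.8 points at π = 0.5, *n* = 140.

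**The case against.** The strongest reply is that this is a slip in illustrative code whose surrounding prose is correct. The plan says the completed datasets are the ones analysed and names the Step B output just before the derivation. The bracketed names are placeholders used loosely: `<OUTPUTDATA>` appears again in Step 4 for the parameter estimates. Read strictly, the code stops before any biased result, because `<Inpdata>` does not exist; harm needs a programmer who copies the SET line and repairs the Step 3 name. The affected group may be empty, since SAP 6.5 allows exclusion from the Per Protocol set for insufficient efficacy data. The public copy of the Step 2 list also breaks off mid-sentence, so further reset rules cannot be ruled out. The error would probably be noticed, through zero between-imputation variance or by comparison with the observed-value response tables in SAP 17.2.3.

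Much of this stands. The method is not wrong, the effect is probably small, and the endpoints are secondary with no margin. It does not remove the contradiction, because section 17.2 is the only code the plan supplies and the one derivation shown reads the wrong file. The cut-off list does not matter either: the point is limited to patients whom Step 2 does not reset, and the plan's use of multiple imputation presupposes that such patients exist.

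**Conclusion.** The concern holds, and should be fixed. As printed, the derivation of Week 28 response reads data in which Week 28 is not yet imputed, and it turns missing scores into responses. The consequence is conditional on three things: the SET line is programmed as shown, its output feeds Step 3, and at least one Per Protocol patient lacks a Week 28 score after Step 2.

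Under the assumed ranges, the overstatement is 0.1 to 4.0 points per arm. Even the top of that range is below the smallest half-width calculated above, and the share affected may be near zero. The between-arm difference moves only if the arms differ in the number affected or in their true response rate. The primary PK analysis is untouched.

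**What to change.** - Make the SET statement of the response derivation read the Step B output, and spell that dataset's name one way throughout.
- Carry the derived dataset under one name through Step 2 and into Step 3, in place of `<Inpdata>`, and do not reuse the Step B name for the Step 4 estimates.
- As a safeguard, add a missing-value condition to the PASI and sPGA IF statements, at every PASI threshold, and confirm that no Week 28 response is missing after Step B.

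The cost is a few dataset names in the sample code and one optional check. Data, design and method do not change, and the code then matches what the SAP text already says.

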#### • Step 2: Non-responder imputation

Patients will be considered as non-responder if

- discontinued the study treatment before Week 28
- lost to follow up before Week 28 (As per End of study CRF page)
- any severe violation related to any therapy that may significantly impact efficacy assessment before
   Week 28 (which will be decided during

#### Step 3: Calculation of proportion in each treatment arm for each imputed data set

PROC FREQ DATA=<Inpdata>;

TABLES <PASI X Category> /binomial(LEVEL=1 CL=WALD) alpha=0.10;

BY Imputation <treatment group>;

ODS OUTPUT BINOMIAL=prop;

RUN:

### Step 4: Combining proportion estimates in each treatment arm and the difference between proportions

For the proportions, the proportion estimates and their asymptotic standard errors provided by PROC FREQ for each imputed data set can be passed directly to PROC MIANALYZE.

PROC MIANALYZE DATA=<PROP> ALPHA=.10;

MODELEFFECTS < Proportion>;

STDERR <Standard error>;

Document: \\ieedc-vnasc01\Biosdata\Viatris\HULIO\HAB34991\Biostatistics\Documentation\SAP

Author: Version Number: 2.0

Version Date: 29Nov2023

Template No.: CS\_TP\_BS016 Revision 7 Reference: CS\_WI\_BS005

Effective Date: 01Nov2021

Page 32 of 48

BY <treatment group>; ODS OUTPUT PARAMETERESTIMATES=<OUTPUTDATA>; RUN:

For the difference between proportions in two arms, the standard error of the estimated difference is computed as the square root of the sum of squared standard errors for each proportion. This standard error is then passed to PROC MIANALYZED along with the estimated difference in proportions.

Step 5: Compute estimates of the difference in proportions of responders between treatment arms and their standard errors

```
DATA prop diff;
MERGE < Treatment group 1 data > < Treatment group 2 data >
BY Imputation;
prop diff = (p1-p2);
se_diff = sqrt(se1*se1 + se2*se2);
RUN;
```

Step 6: Combine estimates of the proportion differences

```
PROC MIANALYZE DATA=prop_diff> ALPHA=.10;
MODELEFFECTS  diff>;
STDERR <se diff>;
ODS OUTPUT PARAMETERESTIMATES=mian_prop_diff;
RUN;
```

